Study protocol. Statistical analysis and results.

Title: Identification of Epidural Space: A Comparison Study Between Contrast Spread and Loss of Resistance Techniques

REB tracking number: 19-06-002

Date of document: 07/17/2020

The study protocol.

The study participants were patients of Astoria Pain Management, New York, USA (age 28–72 years) with a clinical diagnosis of cervical radiculitis. The Canadian SHIELD Ethics Review Board approved this study (July 18, 2019. REB tracking number: 19-06-002), conducted from August 19, 2019, to October 8, 2019. Patients were eligible for the study if they met the criteria for cervical ESI, which included clinical and recent MRI findings confirming the diagnosis of cervical radiculitis and inadequate pain relief with conservative care for more than 3 months. Other criteria were if the procedure was covered by medical insurance, and if they signed informed consent. Patients were excluded from the study if they were taking anticoagulants or had serious comorbidities such as congestive heart failure.

The patients were divided into two groups of 20 each and underwent CESI with either an 18G or a 25G Tuohy needle. Patient selection for the18G and 25G groups was not random. For example, the preference was given for a 25G needle when the procedure was performed at the C5-6 level (25G/18G = 15/4) and for an 18G (18G/25G = 16/5) when the needle was inserted at C6-7 or C7-T1 level. The smaller needles were favored for females (25G/(25G+18G) = 17/24) vs. males (25G/(25G+18G) = 3/16). The skin was anesthetized with 1% lidocaine in the 18G group but not in the 25G group. All CESIs were performed utilizing the fluoroscopy only method when the needle was navigated from the skin toward the epidural space under contralateral obligue fluoroscopy, and the contrast spread technique was employed for epidural space identification. After radiological confirmation of the epidural spread, LOR was tested using an Epidrum® device (Exmoor Innovations Ltd., Somerset, UK). Subsequently, accompanied by the radiology assistant, I observed the Epidrum for 30 seconds or more; if the Epidrum deflated, the result was positive. However, if the device remained inflated, the result was reported as negative. The collected data was then analyzed.

Statistical analysis and Results.

There were three investigations:

1) Within group 1; 18G (LORT vs. CST),

2) Within group 2; 25G (LORT vs. CST); and

3) Between groups 1 and 2 (LORT 1 vs. LORT 2).

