The Confidence Interval Test for Proportion to estimate the confidence interval (CI) between LORT and CST within groups 1 and 2 was employed. The 95% CI was [0.385, 0.815] for group 1 (LORT 60%; 18G) and [-0.031, 0.231] for group 2 (LORT 10%; 25G), confirming that LORT showed a statistically significant lower rate of epidural space detection than CST within each group (Table 1).

Table 1. The 95% Confidence Interval test for proportions of epidural space detection by LORT within 18G and 25G groups.

	Х	n	р	Margin of error for 95% Cl	Lower Limit	Upper Limit
LORT 18G	12	20	60	0.215	0.385	0.815
LORT 25G	2	20	10	0.131	-0.031	0.231

Rate of epidural space detection by CST in both groups is 100%. The 95% Confidence Interval test for proportions confirmed that epidural space detection by LORT is significantly lower than the CST. x–positive results, n–number of patients, p–percentage of positive results.

The z-test for independent proportions was utilized to compare the epidural space detection between LORT 1 (group 1; 18G) and LORT 2 (group 2; 25G). Since CST detected 100%, it was employed as a benchmark to conduct a hypothesis test of proportion, using H₀: ρ = 1; Ha: ρ < 1. There was a statistically significant difference between the proportions of epidural space detection by LORT with 18G compared to 25G needles: z = 3.31, p < 0.001, Cohen's h = 1.13 (Table 2).

Table 2. Z-test for independent proportions for the difference in the epidural space detection by LORT between 18G and 25G groups.

		Х	n	р	
LOR	T 18G	12	20	60	
LOR	T 25G	2	20	10	
Significance level	Pooled proportion	z	p-value	Effect size Cohen's h	
0.05	0.35	3.31	0.0009	1.13	

CST=20 (100%) was employed as a benchmark. Since p-value: 0.0009 < 0.05, H₀ was rejected. As Cohen's h > 0.8, the difference in LORT detection rate between 18G and 25G needles is large.

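### Table 1's interval is described as comparing LORT with CST, but it is a one-sample Wald interval for LORT alone, and at 2/20 its limits are wrong

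*Combined protocol and SAP*

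**What the plan says.** Three investigations are listed under Statistical analysis and Results. The first two are within-group: "Within group 1; 18G (LORT vs. CST") and "Within group 2; 25G (LORT vs. CST"). The protocol part gives the sample size, "The patients were divided into two groups of 20 each", and the order of the two tests: "After radiological confirmation of the epidural spread, LOR was tested" with the Epidrum device. Each patient therefore has both results at one needle placement.

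The stated purpose of the interval is "to estimate the confidence interval (CI) between LORT and CST within groups 1 and 2". For 18G the result reads "The 95% CI was [0.385, 0.815] for group 1 (LORT 60%; 18G"). For 25G the limits are -0.031 and 0.231, with LORT at 10%. The same sentence takes these intervals as confirming a significantly lower detection rate for LORT than for CST in each group.

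Table 1 has one row per needle gauge, holding only the LORT count, n, percentage, margin and limits. CST enters only through the note below it: "Rate of epidural space detection by CST in both groups is 100" per cent.

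**The concern.** The description and the numbers refer to different quantities. An interval comparing two methods should be an interval for their difference, centred on 40 points for 18G and 90 points for 25G. The printed intervals are centred on 0.60 and 0.10, the LORT proportions themselves. The difference that investigations 1 and 2 ask for is never given an estimate or an interval; the reader has to construct it.

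The 25G interval also goes below zero, which a proportion cannot do. That shows the normal approximation has broken down at 2 positives out of 20, so the upper limit needs checking too. The upper limit matters more, because it says how often LORT might still be positive with a 25G needle once contrast has confirmed placement.

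**Working it through.** **Inputs.** n = 20 per group (protocol part); LORT positives 12 (18G) and 2 (25G), and CST 100% in both groups (Table 1 and its note); LOR tested only after contrast confirmation (protocol part). All intervals are two-sided 95%, z = 1.96.

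**1. Reproduce Table 1.** One-sample Wald: p ± 1.96 × √(p(1 − p)/n).
- 18G: 1.96 × √(0.6 × 0.4/20) = 0.2147, giving 0.385 to 0.815.
- 25G: 1.96 × √(0.1 × 0.9/20) = 0.1315, giving -0.031 to 0.231.

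Both match the printed margins and limits. CST does not enter the formula.

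**2. Relation to the paired difference.** Let b be patients positive on CST only and c patients positive on LORT only. Then b = 20 − 12 = 8 and 20 − 2 = 18, and c = 0 in both groups. The standard error of the paired difference is √((b + c) − (b − c)²/n)/n.
- 18G: √(8 − 64/20)/20 = √4.8/20 = 0.1095, equal to √(0.24/20).
- 25G: √(18 − 324/20)/20 = √1.8/20 = 0.0671, equal to √(0.09/20).

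So the paired Wald interval for CST minus LORT is one minus the Table 1 limits: 0.185 to 0.615 (18G) and 0.769 to 1.031 (25G). The second passes 100 points.

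**3. Intervals suited to these counts.** Wilson: centre (p + z²/2n)/(1 + z²/n), half-width z√(p(1 − p)/n + z²/4n²)/(1 + z²/n), with 1 + z²/n = 1.192.
- 18G: 0.584 ± 0.197.
- 25G: 0.164 ± 0.137.

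Clopper-Pearson limits come from beta quantiles: the 2.5% point of Beta(x, n − x + 1) and the 97.5% point of Beta(x + 1, n − x).

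| LORT positivity | Table 1 (Wald) | Wilson | Clopper-Pearson |
|---|---|---|---|
| 18G, 12/20 | 0.385 to 0.815 | 0.387 to 0.781 | 0.361 to 0.809 |
| 25G, 2/20 | -0.031 to 0.231 | 0.028 to 0.301 | 0.012 to 0.317 |

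The 25G upper limit is too low by 0.301 − 0.231 = 0.070 (Wilson) or 0.317 − 0.231 = 0.086 (exact).

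**4. Shortfall from CST, as one minus each limit.**

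| CST minus LORT | Estimate | From Table 1 | Wilson | Exact |
|---|---|---|---|---|
| 18G | 40 points | 19 to 61 | 22 to 61 | 19 to 64 |
| 25G | 90 points | 77 to 103 | 70 to 97 | 68 to 99 |

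**The case against.** The best defence is that Table 1 estimates the right quantity under a loose description. Its title and row labels say LORT, and the text prints the 10% beside the 25G interval, so few readers would take -0.031 to 0.231 as a difference. That stands. A reader might argue that the 25G interval contains 0 and so shows no difference between methods, but the adjacent 10% and 100% rule that reading out.

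Two stronger readings are tempting, and the documents support neither.

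- **That the paired comparison was never analysed.** LOR was tested only after contrast had confirmed spread, so a patient positive on LORT only cannot occur. With that cell empty, the Table 1 interval is the exact mirror of the paired Wald interval (step 2). No pairing information is lost; the discordant counts follow from what is printed.
- **That judging significance by whether the LORT upper limit lies below 100% is too lenient.** The document does not write that rule out; it is inferred. At a hypothetical 16/20 the Wald upper limit is 0.975, while exact McNemar gives p = 2 × 0.5⁴ = 0.125. At 15/20 the figures are 0.940 and p = 0.0625. But uncorrected McNemar gives p = 0.0455 and 0.025, and Tango's paired score interval also excludes zero (0.007 to 0.416 and 0.049 to 0.469). The rule is lenient only against exact or continuity-corrected McNemar. Against the null hypothesis the document states, a detection proportion of 1, a single LORT failure already refutes the null, so the rule is conservative.

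A larger error for 25G could also be claimed. Tango's interval at 18:0 is 0.594 to 0.972, which would put the mirrored Table 1 lower limit of 0.769 about 18 points too high. That interval treats the empty cell as random, whereas the design fixes it at zero. With CST fixed, the gap is 7 to 9 points.

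**Conclusion.** The point holds as a fault of labelling, reporting and interval method. The interval described as a comparison is a one-sample Wald interval for LORT, no LORT-CST difference is reported, and the 25G limits are wrong at both ends. The 18G interval changes by at most about 3 points at either limit.

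The significance statements are unaffected. With 8 and 18 failures out of 20, LORT stays well below 100% in both groups on any of these intervals.

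A reader might infer from the within-group comparison that CST was shown to detect the epidural space better than LORT. The documents do not support this: a contrast-positive placement was the precondition for the LOR test, so 100% for CST is set by the design. For the same reason a McNemar test would add nothing, because its null of equal discordant cells cannot hold when one cell is structurally empty. The informative quantity is LORT positivity given a contrast-confirmed placement.

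This rests on taking the order of testing as stated for all 40 patients, and on CST being treated as fixed at 100%.

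**What to change.** In Statistical analysis and Results and Table 1:

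1. Replace the Wald limits with Wilson or Clopper-Pearson limits, and name the method.
2. Label the interval as LORT positivity among contrast-confirmed placements, and delete the wording that describes it as an interval between the two methods.
3. Report the shortfall from CST as the complement: 40 points (8 discordant patients) for 18G and 90 points (18 discordant patients) for 25G, each with the matching interval from step 4.
4. State that CST is 100% by design because LOR was tested only after contrast confirmation, so the within-group comparison does not show CST superiority. Do not add a McNemar test.

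The cost is a recalculation from counts already printed and a reworded table; no new data are needed. The one downside is a wider 25G interval: 0.262 with the printed limits (0.231 + 0.031), against 0.273 with Wilson (0.301 − 0.028) or 0.305 with Clopper-Pearson (0.317 − 0.012).

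### The 25G detection rate (2 of 20) is given a Wald interval, which yields an impossible negative lower limit and an upper limit 7 to 9 points too low

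*Combined protocol and SAP*

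**What the plan says.** The section Statistical analysis and Results lists three investigations. The second compares loss of resistance (LORT) with contrast spread (CST) within the 25G group. The method for the two within-group investigations is described in one sentence: "The Confidence Interval Test for Proportion to estimate the confidence interval (CI) between LORT and CST within groups 1 and 2 was employed". No formula is given.

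The results text then reports "The 95% CI was [0.385, 0.815] for group 1 (LORT 60%; 18G" and, for the other group, "0.031, 0.231] for group 2 (LORT 10%; 25G". The last quote omits the minus sign that precedes its first figure in the document. The Table 1 row shows the sign: "LORT 25G 2 20 10 0.131 -0.031 0.231". Its columns are positives, patients, percentage, margin of error, lower limit and upper limit.

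The footnote to Table 1 supplies the comparator, "Rate of epidural space detection by CST in both groups is 100" percent, and draws the inference: "The 95% Confidence Interval test for proportions confirmed that epidural space detection by LORT is significantly lower than the CST". The negative limit appears in both text and table without truncation or comment, and no score or exact interval is given anywhere.

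**The concern.** A confidence interval for a proportion should lie between 0 and 1. When some positives have been observed, it should also exclude 0. The 25G interval fails on both counts, which suggests a symmetric normal approximation used where it does not work: n·p = 20 × 0.10 = 2.

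The negative limit is the visible symptom. The less visible one is on the other side. A symmetric interval around a small proportion is too short upwards, so it understates how high the true rate could be. Cutting the lower limit off at 0 would leave that fault in place.

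At stake is the stated precision of the 25G detection rate. A reader is told that loss of resistance with the finer needle succeeds at most about 23% of the time, when the data are compatible with about 30%. The error also leans towards a lower apparent LORT rate, which is the direction of the document's own claim.

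**Working it through.** **Inputs.** Group size is 20 (protocol text: "The patients were divided into two groups of 20 each"). Positives are 2 in the 25G group and 12 in the 18G group (Table 1). The confidence level is 95% with two limits reported, so z = 1.96.

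**Step 1: reproduce the document's figures.** Wald interval, p ± 1.96·√(p(1−p)/n):

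- 25G: √(0.10 × 0.90 / 20) = 0.0671; margin 1.96 × 0.0671 = 0.1315; limits −0.0315 and 0.2315. Table 1 has a margin of 0.131 and takes 0.10 ± 0.131.
- 18G: √(0.60 × 0.40 / 20) = 0.1095; margin 0.2147; limits 0.3853 and 0.8147. Table 1 has 0.215, 0.385 and 0.815.

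Both rows match to rounding. For 2 of 20, a continuity-corrected Wald interval (−0.056 to 0.256) and a t-based margin (0.140) do not match. That the method is Wald is an inference from this match, since the document does not say so.

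**Step 2: recompute with methods suited to small counts.** The Wilson interval is [p + z²/(2n) ± z·√(p(1−p)/n + z²/(4n²))] / (1 + z²/n), with z² = 3.8415.

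- 25G: centre (0.10 + 0.0960)/1.1921 = 0.1645; half-width 0.1366; limits 0.028 and 0.301.
- 18G: centre (0.60 + 0.0960)/1.1921 = 0.5839; half-width 0.1973; limits 0.387 and 0.781.

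The Clopper-Pearson limits are the rates at which each binomial tail beyond the observed count equals 0.025.

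| Method | 25G (2/20) | 18G (12/20) |
|---|---|---|
| Wald (as reported) | −0.031 to 0.231 | 0.385 to 0.815 |
| Wilson | 0.028 to 0.301 | 0.387 to 0.781 |
| Clopper-Pearson | 0.012 to 0.317 | 0.361 to 0.809 |
| Jeffreys | 0.021 to 0.284 | 0.384 to 0.789 |
| Mid-P | 0.017 to 0.293 | 0.379 to 0.794 |
| Agresti-Coull | 0.016 to 0.313 | 0.386 to 0.782 |

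The 25G upper limit falls short by 0.301 − 0.231 = 0.070 against Wilson and by 0.317 − 0.231 = 0.086 against Clopper-Pearson. Jeffreys gives the smallest gap, 0.284 − 0.231 = 0.053.

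**Step 3: test the reported upper limit directly.** If the true rate were 0.231, the chance of 2 or fewer positives in 20 would be 0.005 + 0.031 + 0.090 = 0.126. At a two-sided 95% upper limit this tail should be about 0.025, so it is about five times too large. At 0.317 it is 0.025.

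**Step 4: exact coverage at n = 20.** For each true rate, add the binomial probabilities of the counts from 0 to 20 whose interval contains that rate.

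| True rate | Wald | Wilson |
|---|---|---|
| 0.05 | 63.9% | 92.5% |
| 0.10 | 87.6% | 95.7% |
| 0.15 | 81.9% | 97.8% |

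At a true rate of 0.10, Wald misses 100 − 87.6 = 12.4% of the time. Of that, 12.2 points are intervals whose upper limit falls below the truth.

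**The case against.** The strongest reply is that nothing the document concludes depends on the choice. The intervals serve one purpose, to show that LORT detection is below the 100% benchmark, and for that only the distance of the upper limit from 1 matters. For 25G the upper limit is at most 0.32 by any method, and for 18G it is about 0.81 or lower. The between-group comparison (z = 3.31, p = 0.0009, Table 2) does not use these intervals, and Fisher's exact test on the same counts gives p = 0.0022. All of this stands.

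The 18G row is also hardly affected. Wald and Clopper-Pearson upper limits differ by 0.815 − 0.809 = 0.006, and Wald coverage at a true rate of 0.60 is 92.8%. This stands too: changing that row is a matter of consistency.

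The size of the shortfall depends on the comparator. It is 7 to 9 points against the two methods recommended here and about 5 against Jeffreys. All the alternatives examined lie above 0.231, so the direction is not in doubt. The coverage of 63.9% belongs to a true rate of half the observed one; the figure nearest the data is 87.6%. Wilson is not perfect either, at 92.5% for a true rate of 0.05.

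Finally, a better interval for one proportion does not turn it into a comparison of LORT with CST. Loss of resistance was tested only after contrast had confirmed the position, so the 100% benchmark follows from the design. That is a separate matter, and the proposed change does not address it.

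None of this defends the printed interval. Its arithmetic is right, but the method does not suit 2 events in 20.

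**Conclusion.** The concern holds. The reported 25G interval has an impossible lower limit, includes a rate of zero that two positives exclude, and has an upper limit 7 to 9 percentage points below the Wilson and Clopper-Pearson values. Its coverage near the observed rate is 87.6%, not 95%.

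The consequence is limited to precision: the finding that LORT detects less often than the benchmark is unchanged. It should still be corrected, because Table 2 concerns the between-group comparison and this interval is therefore the only numerical inference reported for the second investigation.

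The verdict rests on two assumptions: that the 20 results in a group are independent with a common detection rate, and that the unnamed formula is Wald. The second affects only the explanation, since the printed limits are faulty however they were obtained.

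**What to change.** Replace the limits in both rows of Table 1 and in the results text with Wilson intervals, and name the method:

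- 18G: 60%, 95% CI 0.387 to 0.781
- 25G: 10%, 95% CI 0.028 to 0.301

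Clopper-Pearson is an acceptable alternative if guaranteed coverage is preferred (0.361 to 0.809 and 0.012 to 0.317). Use the same method in both rows. Remove the margin-of-error column, because these intervals are not symmetric about the estimate.

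The cost is recalculating two intervals from counts already in the table. The only drawback is that the result can no longer be written as an estimate plus or minus a single number.
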